1. OBJECTIVES

1.1 Primary Objectives

The primary objective of the study is to test for the equivalency of the two aspirin schedules. We are going to evaluate the effects of a 3-month intervention of continuous versus intermittent aspirin dosing (i.e. 325 mg daily and 325 mg 3 weeks on/3 weeks off) on the ratio of cell proliferation (Ki-67) /apoptosis (BAX) in rectal biopsies.

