In addition to using aspirin every other day, as mentioned in the NCI TORFP BB-2015, previous animal studies have examined other intermittent dosing strategies in carcinogenesis models⁴⁰. Very recently, a DCP-sponsored rodent study found aspirin delivered on an intermittent schedule (i.e. 3 weeks on followed by 3 weeks off) had an equally high efficacy in preventing colon cancer with aspirin delivered continuously. This is a novel strategy. If confirmed in human studies, it may be able to minimize the adverse event and simultaneously maximize the high efficacy.

Apoptosis Mounting evidence from *in vitro*, *in vivo* and human studies indicates acquired resistance to apoptosis is one hallmark for almost all cancer types⁴¹. The maintenance of normal colorectal crypt architecture is based on the balance between the apoptosis at the base of crypts and the proliferation at the top⁴². *The transformation from normal colorectal epithelium to carcinoma is accompanied by a progressive resistance to apoptosis*⁴³. [name] group found in a prospective study that subjects with the highest tertile level of apoptosis in normal rectal mucosa had a 70% reduction in risk of future colorectal adenoma, compared to the lowest tertile level of apoptosis⁴⁴. Terminal deoxyribonucleotidyl transferase-mediated dUTP nick end labeling (TUNEL) and BAX expression⁴⁵ was used to measure apoptosis.

Biomarker for proliferation (Ki-67) Cell proliferation is another critical factor in tumorigenesis⁴⁶. As we mentioned earlier, the balance between apoptosis and proliferation maintains the normal colorectal crypt architecture⁴². Cell proliferation index has been used in many previous intervention trials to assess the effects of chemoprevention agents⁴⁷ while Ki-67 is one of the most frequently used natural proteins associated with proliferation⁴⁶. We have identified one published study which found aspirin treatment significantly reduced cell proliferation in young people with familial adenomatous polyposis compared to placebo arm⁴⁸.

Therefore, **we hypothesize** that 325 mg aspirin delivered 3 weeks on/3 weeks off has the same efficacy in increasing colorectal apoptosis, reducing colorectal cell proliferation and, in turn, decreasing cell proliferation/apoptosis ratio as aspirin delivered 325 mg daily, but confers reduced side-effect, i.e. gastrointestinal bleeding.

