13. STATISTICAL CONSIDERATIONS

13.1 Study Design/Description

This is a Phase IIa, 3 arm, randomized placebo-controlled trial (40 subjects in each of two treatment arms and 10 subjects in the placebo arm) to evaluate whether, use of aspirin at 325 mg in a three weeks on/three weeks off regimen has similar/equivalent efficacy. Our hypothesis is that intermittent use group will show equivalent reduction in the primary endpoint (proliferation: apoptosis ratio) and reduced risk of adverse events, as that using aspirin daily.

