13.4 Primary Objective, Endpoint(s), Analysis Plan

The primary endpoint will be the ratio of proliferation to apoptosis biomarkers (Ki67 index: BAX index, measured continuously) in colorectal mucosa. We anticipate that the two treatment arms are “equivalent” with regard to this main outcome, in the manner described below, for which power analysis is provided. The statistical analysis will consist of examining whether two means are within prescribed limits from each other. Alternatively, two one sided tests can be performed. We have $n_1=n_2=32$, which is 40 less 20% dropout; $40-8=32$.

Power analysis for the main outcome

The main outcome is defined as the ratio $R = P/A$, where P for measure of Proliferation and A stands for measure of Apoptosis. In principle, intervention increases the Apoptosis and decreases Proliferation,

resulting in R decreasing.

We will measure R for each subject, in each treatment group at baseline (Clinic Visit 2) and at three months (Clinic Visit 4; 12 weeks), obtaining $R(i, j)$, where $i = 0, 3$ months is the time point, and $j = 1, 2$ represents the treatment arm. We will then obtain within-subject changes $D(j) = R(3, j) - R(0, j)$ for each subject. We expect R to decrease in both groups.

We will then compare mean changes in R between arms to show their equivalence, which we expect, is supported by statistical evidence. To this end, we compute power of a test of equivalence, as defined by following considerations.

The existing information on $R = P/A$ is scant. From [name] ongoing R01 randomization trial (R01 CA149633; PI: [name]) we have that $CV = SD/\text{mean of distribution of } R$ is in the range of 1.5-2 (150-200%).

Variable	Mean	Std Dev
A_P_overall	0.1825	2.5884
A_P_surface	3.2685	4.6094
A_P_bottom	0.0679	3.7236
P_A_overall	2.5444	4.0427
P_A_surface	0.306	4.6094
P_A_bottom	14.733	3.7236

This will limit our ability to argue in favor of equivalence using the usual cutoff points of 10% and 20%. Thus we will have to settle on a broader interval, namely that of 3/4 of standard deviation previously observed in the similar data.

We will assume the correlation between time = 0 and time = 3mo to be $\text{Corr}[R(3, j), R(0, j)] = 0.5$. Simple calculation shows that if pre and post variances are equal to each other σ^2 , then $\text{Var}[D(j)] = \sigma^2$, and thus theoretical standard deviation $SD[D(j)] = \sigma$.

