13.5 Secondary and Exploratory Objectives, Endpoints, Analysis Plans

The secondary objectives are to evaluate the effects of aspirin treatments on:

- 1) the ratio of cell proliferation (Ki-67)/apoptosis (TUNEL) in rectal biopsies
- 2) the ratio of cell proliferation (Ki-67)/necroptosis (pMLKL) in rectal biopsies
- 3) fecal occult blood test (measures of adverse events) as measured by stool samples

The exploratory objectives are to evaluate the effects of aspirin treatments on:

- 1) COX-2 in rectal biopsies
- 2) BAX in rectal biopsies
- 3) TRPM7 in rectal biopsies
- 4) joint index of COX-2 with TRPM7 expression in rectal biopsies;
- 5) joint index of TRPM7 with BAX in rectal biopsies;
- 6) methylation assays using the MethylationEPIC BeadChip to identify methylation biomarkers in genes (i.e. CDKN2A (cell cycle regulation), MGMT (DNA repair), DAPK1(apoptosis), CDH1(cell invasion), WNT16 (Wnt pathway) and RASSF1 (RAS signaling)) involved in colorectal carcinogenesis, and other epigenome-wide methylation biomarkers as measured in rectal biopsies;
- 7) metagenomics analysis to measure abundance of *E. coli* and *Fusobacterium* and other microbiota in rectal swabs

The majority of secondary and exploratory endpoints are continuous. Biomarker levels at baseline, 9 and 12 weeks, as well as the corresponding changes from baseline, will be summarized using descriptive statistics including means and standard deviations or medians and interquartile range, as well as graphical methods such as “spaghetti plots” that depict change patterns over time. Distributions of each marker will be examined, and values may be transformed as needed to stabilize the variance or satisfy the normality assumption. Correlation between biomarkers, and between pre- and post-treatment values will be examined using scatterplots with overlayed smoother plots for ease of visual interpretation.

If the normality assumptions are satisfied, paired t-tests will be used to examine whether the biomarkers change from baseline to 12 weeks post-treatment in each treatment arm. Signed rank test will be used if no suitable transformation can be found. Because we expect that the continuous and intermittent dosing regimens will result in similar biomarker changes, we will use the TOST procedure, similar to the primary

endpoint, to test for equivalence. The equivalence margin will be set as 3/4 of the observed standard deviation of the marker at baseline, similar to the primary endpoint.

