Additional analyses will be conducted using linear mixed effects models with repeated measures to further explore biomarker change patterns over time across 3 time points, and to compare them between arms. These models use all available observations accommodating data that are missing at random, rather than performing a complete case analysis.

A placebo arm is included in the secondary analyses because the variations on repeated measurement of the new biomarkers of methylation and microbiota are not known from the previous trials, and therefore changes in the treatment arms are difficult to interpret. The placebo arm is used as a reference for background, as a cohort for analysis.

Fecal occult blood tests will be categorized as binary (present vs. absent) at each time visit. Proportion of patients with at least one positive test will be compared between arms using Fishers exact test because incidence of this adverse event is expected to be low.

Exploratory endpoints of joint index of COX-2 with TRPM7 and joint index of TRPM7 with BAX in rectal biopsies will be analyzed similarly. Indices will be calculated using a scoring approach based on factor analysis.

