13.8 Evaluation of Response

All participants included in the study will be assessed for response to intervention, even if there are major protocol deviations.

All of the participants who met the eligibility criteria, receive the study agent will be included in the intention-to-treat analysis. Since we will collect rectal biopsies at baseline, week 9 and 12, we will include the participants in the analysis if he/she provides biopsies at week 0 and week 9, but not week 12. Participants will be excluded if he/she only provides one biopsy. All conclusions regarding efficacy will be based on these participants.

Subanalyses may be performed on the subsets of participants, excluding those for whom major protocol deviations have been identified (e.g., early death due to other reasons, early discontinuation of intervention, major protocol violations, etc.). However, subanalyses may not serve as the basis for drawing conclusions concerning efficacy, and the reasons for excluding participants from the analysis

should be clearly reported. For all measurements of response, the 95% confidence intervals should also be provided.

We will conduct analysis by the grade of adenomas.

Biomarkers from Week-9 biopsies will also be used in the subanalysis in the intermittent arm.

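### The hypothesis is an equivalent reduction in Ki-67/BAX, but no rule in section 13.4 ties the equivalence result to a shown fall in either aspirin arm

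*Combined protocol and SAP*

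**What the plan says.** The objective in section 1.1 concerns the two schedules only: "The primary objective of the study is to test for the equivalency of the two aspirin schedules". The hypothesis goes further. Section 13.1 expects that the "intermittent use group will show equivalent reduction in the primary endpoint", and section 2.3 that the intermittent schedule "has the same efficacy in increasing colorectal apoptosis, reducing colorectal cell proliferation and, in turn, decreasing cell proliferation/apoptosis ratio" as the daily one.

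Section 13.4 defines the primary analysis as two one-sided tests (TOST) on the between-arm difference in mean change in R from baseline to week 12: "The statistical analysis will consist of examining whether two means are within prescribed limits from each other". A fall in R appears there as an expectation, "We expect R to decrease in both groups", and not as a condition of success.

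Four other provisions bear on whether R fell:

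- Section 13.8: "For all measurements of response, the 95% confidence intervals should also be provided".
- Section 13.8 also plans a subanalysis of week-9 biopsies in the intermittent arm.
- Section 13.5: "paired t-tests will be used to examine whether the biomarkers change from baseline to 12 weeks post-treatment in each treatment arm". This stands under the secondary and exploratory markers, which include Ki-67/TUNEL, Ki-67/pMLKL and BAX but not Ki-67/BAX.
- Section 13.5, on the 10 placebo participants: "The placebo arm is used as a reference for background, as a cohort for analysis".

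**The concern.** Because the test uses only the difference between the aspirin arms, a shared change of any size or direction drops out. If neither schedule affects R, the expected primary result is still equivalence, and nothing in section 13.4 prevents that being reported as equal efficacy. The plan itself says that little is known about R, so a fall cannot be taken for granted.

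Timing adds a reason for care. If the active block comes first, as the wording of section 3 suggests, the intermittent arm's week-12 biopsy ends a placebo block (weeks 10-12). The week-9 biopsy would end an active block, and the week-9 subanalysis looks at that time point, but it does not condition the primary conclusion.

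**Working it through.** **Inputs (section 13.4).** Mean R 2.54, SD 4.04, pre/post correlation 0.5, SD of change 4.04, 32 per arm (40 less 20%), margin 3/4 SD, alpha 0.05 for each one-sided test.

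**1. Reproduce the plan's power.** Exact two-sample TOST power, 62 degrees of freedom, true difference 0:

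- Margin 2.02, alpha 0.10: 0.519 (plan 0.52).
- Margin 3.03, alpha 0.05: 0.814 (plan 0.81).
- Margin 3.03, alpha 0.10: 0.911 (plan 0.91).

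**2. Log scale.** SD_log = sqrt(ln(1 + (4.04/2.54)^2)) = 1.1231. Margin = 0.75 x 1.1231 = 0.8423, a ratio of 0.43 to 2.32. Power is 0.814, or 0.817 with the SD rounded to 1.12. If the correlation of 0.5 holds on the raw scale instead, the log correlation is 0.648 and the SD of change is 1.1231 x sqrt(2 x (1 - 0.648)) = 0.94.

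**3. Two inert arms.** Power depends only on the true difference, so inert arms give the planned power: 81% at SD 1.12 and 94% at SD 0.94. On the raw scale, simulation (400,000 trials) gives 81% whether both arms change by 0, by -4.04 or by +4.04. With a true difference equal to the margin, equivalence is declared in 5% of trials.

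**4. Inert intermittent arm, effective daily arm.** The plan's one-SD fall, carried to the log scale, is a cut of 1 - exp(-1.1231) = 67%. Equivalence is then declared in about 0.4% of trials. At daily cuts of 30%, 40% and 50% (my assumptions) it is declared in 52%, 32% and 13% at SD 1.12, and 65%, 40% and 15% at SD 0.94.

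**5. Adding a within-arm condition.** Require the two-sided 95% CI for mean log-change to lie below 0 in both aspirin arms. The CI half-width is about 0.405 at SD 1.12, so each arm needs an observed fall of about 1 - exp(-0.405) = 33% (29% at SD 0.94). Chance that TOST and condition are both met:

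| True state | SD 1.12 | SD 0.94 |
|---|---|---|
| Both arms inert | under 0.1% | under 0.1% |
| Both cut 67% | 81% | 94% |
| Both cut 50% | 74% | 92% |
| Both cut 40% | 46% | 70% |
| Both cut 30% | 17% | 30% |
| Intermittent inert, daily cut 30-50% | 1-2% | 1-2% |

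With the condition on the daily arm only, the last row would be 9-13% at SD 1.12 and 14-27% at SD 0.94.

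**6. Drift.** The condition is pre-post. A common drift of 20% or 30% without drug effect meets it, together with the TOST, in about 4% or 17% of trials at SD 1.12, and 6% or 30% at SD 0.94. With 8 placebo completers (10 less an assumed 20%), the placebo CI half-width is 0.94 log units, a factor of about 2.6 each way.

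**7. Planning figures.** The plan treats 2.54 and 4.04 as arithmetic. Then 2.54 - 4.04 = -1.50, which a non-negative ratio cannot reach, and 3.03/2.54 = 1.19, so the margin exceeds the baseline mean. The table leaves some doubt about the scale. Surface and bottom A/P and P/A means are reciprocal (3.2685 x 0.306 = 1.00; 0.0679 x 14.733 = 1.00) with equal SDs, as geometric summaries would be. The overall pair is not (0.1825 x 2.5444 = 0.46). If the figures are geometric, SD_log = ln(4.0427) = 1.40, power at 0.8423 is 54%, and 3/4 SD would be 1.05 (81%).

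**The case against.** The strongest reply is that every equivalence test behaves this way. Power is computed at a true difference of zero, so 81% for two inert arms and 81% planned power are one number seen twice. That stands. A reader might infer from the 81% that the test has an inflated false-positive rate. The documents do not support this, because the TOST holds 5% at the margin.

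A reader might also infer that the primary analysis fails its objective, or that a lack of effect would go unseen. Neither follows. Section 1.1 asks for equivalence of schedules, and the TOST tests that. The 95% CIs, the paired tests on related markers and the week-9 subanalysis would expose a null result. What these provisions lack is any link to the conclusion about efficacy in sections 13.1 and 2.3.

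Nor should one infer that an inert intermittent arm would usually pass. At a one-SD daily effect on the log scale it passes in about 0.4% of trials. The weakness lies at no effect and at smaller effects.

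Finally, a pre-post condition cannot attribute a fall to aspirin, and about 8 placebo completers cannot rule out drift. That limit remains with the rule in place.

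**Conclusion.** The point holds as a gap in interpretation that should be fixed; it does not invalidate the primary test. The hypothesis is an equivalent reduction, while the analysis shows only similar change. On the plan's inputs two inert arms are declared equivalent in about 81% of trials (94% if the SD of change is 0.94), and no pre-specified rule separates that result from equal efficacy. The 81% assumes 32 analysed per arm and the arithmetic reading of 2.54 and 4.04. With 40 analysed per arm it would be about 91%. The main point does not depend on these inputs, because a common change cancels at any SD and margin.

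The impossible 4.04 fall and the wide 3.03 margin are a separate planning matter, conditional on the arithmetic reading. They affect the stated planning figures more than the test likely to be run, since the log fallback is the probable analysis.

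**What to change.** Keep the TOST as the primary test of equivalence and add to section 13.4, before unblinding:

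> Equivalence will be described as an equivalent reduction, or equal efficacy, only if the two-sided 95% CI for mean log-change in R from baseline lies wholly below 0 in both aspirin arms. Otherwise the report will state that the changes were within the margin but no common reduction was shown. The placebo arm's mean log-change and 95% CI will be shown beside them.

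Use the same analysis set, and the same handling of participants without a week-12 biopsy, as the primary TOST. This must be reconciled across the plan: section 13.4 defines change to week 12, section 13.8 keeps participants with biopsies at weeks 0 and 9 only, and section 13.6 imputes missing data.

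Separately, confirm whether 2.54 and 4.04 are arithmetic or geometric. Then make log(R) the primary scale and restate the expected fall, margin and power on it: 0.8423 and 81% if arithmetic; power of 54% at 0.8423 if geometric.

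**Cost.** Plan wording and two intervals from data already collected. All conditions must be met for the reduction claim, so no alpha adjustment is needed. The equivalence result is unaffected. The claim loses nothing at a one-SD log fall, but its chance drops at smaller common effects as tabulated above. A condition on the daily arm alone would keep about 78%, 60% and 33% at common cuts of 50%, 40% and 30% (SD 1.12), at the price of weaker protection against an inert intermittent arm. The sponsor should make that choice openly.

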From [name] data we use $\text{mean}[R(0, j)] = 2.54$; $\text{sigma}[R(0, j)] = 4.04$. We expect a decrease in R in both groups, on average about one standard deviation. Then the difference post-pre = 4.04 in each group, save for statistical variability. For equivalence interval for comparison of treatments 1 and 2, we take 3/4 of the standard deviation, namely 3.03. For 20% expected drop-out, we have $n_1 = n_2 = 32$, power analysis is provided below. We use PASS (www.NCSS.com) for computation. The procedure presented below can be described as follows (PASS Manual, Chapter 260). "This procedure allows you to study the power and sample size of equivalence tests of the means of two independent groups using the two-sample t-test. Schuirmann's (1987) two one-sided tests (TOST) approach is used to test equivalence. For a comprehensive discussion, refer to Chow and Liu (1999)." Essentially, two one sided tests with alpha and beta provide an equivalence test.

Power Analysis of Two-Sample T-Test for Testing Equivalence Using Differences Numeric Results for Testing Equivalence Using a Parallel-Group Design

Reference Treatment	Group Sample	Group Sample	Lower	Upper

Power	Size (N1)	Size (N2)	Equiv. Limit	Equiv. Limit	True Difference	Standard Deviation	Alpha	Beta
0.52	32	32	-2.02	2.02	0.00	4.04	0.10	0.48
0.81	32	32	-3.03	3.03	0.00	4.04	0.05	0.19
0.91	32	32	-3.03	3.03	0.00	4.04	0.10	0.09

The normality assumption for the ratio R will be checked, and data will be logarithmically transformed if the normality assumption does not hold. Assuming log-normal distribution, mean of 2.54 and SD=4.04 on the original scale correspond to mean $m=0.3015$ and $SD_{\log} = 1.12$ on the log-transformed scale. Further assuming equal variances across time points in both treatment arms, and within-subject correlation 0.5 between pre- and post-treatment values (as above), the standard deviation of changes will also be $SD_{D,\log} = 1.12$. The equivalence margin on the log-scale will then be $\delta = 3/4*SD_{D,\log} = 0.8423$.

Based on the TOST procedure, equivalence will be established at $\alpha=0.05$ significance level if the $(1-2\alpha)\times100\%$ CI for the difference is contained within the interval $(-\delta, \delta)$. The overall p-value for the equivalence test will be the larger of the p-values of the two one-sided tests.

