13.6 Reporting and Exclusions

To impute missing data we will use Multiple Imputation via a Semi-Parametric Probability Integral Transformation. This is an approach for imputing continuous, binary, and mixed data by first mapping these data to normally distributed values and then applying multiple imputation so that distributional assumptions for the original data can be relaxed. This method was developed by [name], of Northwestern University, in 2012.

http://indigo.uic.edu/bitstream/handle/10027/8652/[name].pdf?sequence=1

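### The primary equivalence test uses unadjusted change scores; adjusting for baseline at the same fixed margin would raise power from 0.81 to about 0.92 under the plan's own assumptions.

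*Combined protocol and SAP*

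**What the plan says.** Section 13.4 defines R as the Ki-67/BAX ratio, measured at Clinic Visit 2 (baseline) and Clinic Visit 4 (12 weeks), and takes the within-subject change D = R(3) − R(0). The primary comparison of the daily and intermittent arms is then: "We will then compare mean changes in R between arms to show their equivalence". The power procedure is described as "equivalence tests of the means of two independent groups using the two-sample t-test", that is, TOST with no covariate.

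The planning values are SD 4.04 and mean 2.54 for R, equal variances before and after treatment, and correlation 0.5, so that the SD of D is again 4.04. The margin is ±3.03 (three quarters of that SD), with 32 evaluable per arm, true difference 0 and alpha 0.05. Stated power is 0.81.

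On scale, the section says "data will be logarithmically transformed if the normality assumption does not hold". It carries over "within-subject correlation 0.5 between pre- and post-treatment values" to the log scale, with SD 1.12 and margin 0.8423.

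No section puts baseline into the primary test. The only model-based comparison of arms is in section 13.5: "Additional analyses will be conducted using linear mixed effects models with repeated measures".

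**The concern.** A change score subtracts the whole baseline value, which is the best use of baseline only when the regression slope of post on pre is 1. With equal variances the slope equals the correlation, here assumed to be 0.5. At exactly 0.5 the noise added by subtracting baseline cancels the benefit. Below 0.5 the planned test does worse than discarding baseline altogether.

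This matters because 0.81 leaves little room. It requires 32 evaluable participants per arm, a true difference of exactly zero and a correlation of at least 0.5. The correlation is assumed rather than estimated, and section 13.4 itself says that little is known about R. A shortfall on any of these takes power below 80%, and the trial could then fail its primary objective for lack of precision although the baseline biopsies needed to recover much of the loss are already collected.

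**Working it through.** **Inputs (all from section 13.4).** n = 32 per arm; sigma = 4.04; margin 3.03 = 0.75 × 4.04; alpha = 0.05 per one-sided test (90% CI inside the margin); true difference 0; correlation rho = 0.5; equal variances. Log scale: SD 1.123 (the plan rounds to 1.12), margin 0.8423.

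**Power formula.** Equivalence is declared when |estimate| + t(0.95, df) × SE < margin. Power is the probability of this event, integrated over the sampling distribution of the estimated SD.

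**Step 1: reproduce the plan.** SE = 4.04 × √(2/32) = 1.01, df = 62.

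| Margin | Alpha | Stated power | Recomputed |
|---|---|---|---|
| 2.02 | 0.10 | 0.52 | 0.519 |
| 3.03 | 0.05 | 0.81 | 0.814 |
| 3.03 | 0.10 | 0.91 | 0.911 |

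**Step 2: compare the variances.**
- Week-12 value alone: sigma².
- Change score: 2(1 − rho) sigma² = 2 × 0.5 × sigma² = sigma².
- ANCOVA residual: (1 − rho²) sigma² = 0.75 sigma², so SD = 4.04 × √0.75 = 3.499.

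Since 1 − rho² = (1 − rho)(1 + rho) and 1 + rho ≤ 2, the ANCOVA residual variance never exceeds that of the change score. Regressing D or week-12 R on baseline and arm gives the identical arm coefficient, so the margin keeps its meaning.

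**Step 3: ANCOVA power at the fixed margin.** df = 61, with variance multiplied by 1 + 1/60 for estimating the baseline slope. Power is 0.920 (0.925 without that term). The log scale, 0.8423/1.123 = 0.75 SD, gives the same 0.814 and 0.920. The 90% CI half-width, before the slope term, falls from 1.67 × 1.01 = 1.69 to 1.67 × 3.499 × 0.25 = 1.46 (log: 0.469 to 0.406).

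**Step 4: vary the assumptions, margin still fixed at 0.75 sigma.**

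| Scenario | Change score | ANCOVA |
|---|---|---|
| rho 0.3 | 0.612 | 0.850 |
| rho 0.5 | 0.814 | 0.920 |
| rho 0.7 | 0.971 | 0.987 |
| rho 0.5, 25 evaluable per arm | 0.668 | 0.820 |
| rho 0.5, true difference 0.25 SD (1.01) | 0.620 | 0.730 |

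The week-12 value alone has power 0.814 at any rho, so at 0.3 the change score does worse than ignoring baseline.

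**Step 5: simulation with normal data (200,000 trials per correlation).** Change score and ANCOVA: 0.816 and 0.920 at rho 0.5; 0.613 and 0.849 at 0.3; 0.971 and 0.986 at 0.7. Type I error at the margin with rho 0.5 is 0.050 for both.

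**Step 6: what happens if the margin moves.**
- Rescaled to three quarters of the ANCOVA residual SD (0.75 × 3.499 = 2.62): power returns to 0.814, or 0.805 with the slope term. The gain vanishes.
- Log margin recomputed as three quarters of the SD of changes, as the formula in 13.4 could be read: change-score power is 0.81 at any correlation, and ANCOVA gives 0.95 at 0.3 and 0.88 at 0.7.

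**Step 7: what adjustment does not do.** At power 0.814, ANCOVA would allow a margin of about 0.65 to 0.66 SD, or 2.62 to 2.65 raw. Against the baseline mean, 2.62/2.54 = 103%, compared with 3.03/2.54 = 119% now. The margin remains very wide.

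**The case against.** The strongest reply is that nothing here is wrong: the change-score TOST is valid, its power is correctly stated, and 0.81 meets the usual target. That stands. This is a missed efficiency, not an error.

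Second, 0.5 cannot be the correlation on both scales. Under the plan's log-normal assumption, a raw correlation of 0.5 implies about 0.65 on the log scale, where power would be about 0.94 against 0.97, a gain of three points rather than eleven. Conversely, 0.5 on the log scale implies about 0.35 on the raw scale. This is a fair caution about reading 0.92 as applying to both scales at once. Section 13.4 does state 0.5 for the log scale, however, and ANCOVA is ahead in every case.

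Third, adjustment only partly offsets a non-zero true difference: at 0.25 SD power is still 0.73. That also stands.

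Fourth, the gain depends on fixing the margin, while the log formula in 13.4 ties it to the SD of the analysed change. This is answered by stating the printed values as fixed.

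Fifth, the two analyses target the same difference under randomisation, but section 13.8 drops participants with only one biopsy. If dropout differs by arm and unbalances baseline, the two estimates can diverge. That limit is real and is one reason to report both.

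The mixed models in section 13.5 do not answer the point, since they are additional analyses and do not decide the primary claim.

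**Conclusion.** The concern holds as a worthwhile and inexpensive improvement. Under the plan's own assumptions, baseline adjustment raises power from 0.81 to about 0.92 at the same margin and type I error. About 25 evaluable participants per arm with adjustment then do the work of 32 without it (0.820 against 0.814). The benefit is larger if the correlation is below 0.5 and small if it is well above.

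The figures rest on equal variances, a linear relation with baseline, normality on the analysed scale and a margin held at its printed value. Raw-scale normality is doubtful, as the SD exceeds the mean (4.04/2.54 = 1.59), so the log-scale figures are the safer ones. Adjustment lessens the effect of lost participants, a lower correlation or a small true difference. It does not remove that effect, and it does not resolve the width of the margin.

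**What to change.** In section 13.4:

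- Make the primary analysis an ANCOVA of week-12 R on baseline R (Clinic Visit 2) and arm, comparing the daily and intermittent arms, on the scale set by the existing normality rule (baseline and week 12 both logged if the log scale is used).
- Declare equivalence at alpha 0.05 if the 90% CI for the adjusted arm difference lies within ±3.03 (raw) or ±0.8423 (log). State that these margins are fixed and are not recomputed from the residual SD.
- Keep the change-score TOST as a sensitivity analysis.

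The inclusion rule in section 13.8 can stay: "we will include the participants in the analysis if he/she provides biopsies at week 0 and week 9, but not week 12". Say explicitly that such participants enter through imputation of the week-12 value by the method already named in section 13.6: "To impute missing data we will use Multiple Imputation via a Semi-Parametric Probability Integral Transformation".

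Use the same baseline-adjusted model for the secondary biomarker TOSTs in section 13.5. Their margin is unaffected by adjustment: "The equivalence margin will be set as 3/4 of the observed standard deviation of the marker at baseline". The gain there is unknown, because the documents give no pre/post correlation for those markers.

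The cost is one degree of freedom and a change of wording, which goes through the amendment approvals in section 14.3 and should be settled before the data are seen. No new data, visits or participants are needed.
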